1.2 DRUG PROFILE

Drug Substance and Drug Product

Neihulizumab (AbGn-168H) is derived from AbGn-168, a humanized monoclonal antibody of the IgG4 subclasses which binds to human CD162 (PSGL-1). The AbGn-168H molecule is composed of two heterodimers. Each of the heterodimers is composed of a heavy and a light polypeptide chain. The four polypeptide chains of the antibody molecule are linked together by disulfide bonds. In order to reduce the *in vivo* occurrence of half molecules (also known as shuffling) of wild type IgG4 antibodies such as AbGn-168, a serine to proline (S228P) mutation was introduced in the hinge region of AbGn-168H heavy chain by PCR mutagenesis. This mutation was shown to stabilize the intermolecular disulfide bonds and eliminate IgG4 shuffling *in vivo*. The heavy chains are glycosylated and there are two binding sites for CD162 per antibody molecule. The antibody protein has a molecular mass of approximately 148 kDa.

AbGn-168H is expressed in Chinese hamster ovary (CHO) cells. It is manufactured using standard mammalian cell culture techniques, followed by a series of protein purification steps including several chromatography steps, as well as steps for removal and inactivation of potential viruses.

The current formulation of the AbGn-168H drug product is a solution for injection at a concentration of 40 mg/mL.

Pharmacology and Safety Pharmacology

AbGn-168H binds to PSGL-1 and preferentially induces apoptosis of activated T cells and spares primary peripheral T cells, the majority of which are resting T cells. The *in vivo* pharmacologic effects have been demonstrated in a murine model of DTH (*trans-vivo* Delayed-type Hypersensitivity) and a DTH model in cynomolgus monkey, the relevant animal species, indicating a pharmacologically relevant effect can be achieved *in vivo*.

As an IgG4 antibody, AbGn-168H does not mediate ADCC (Antibody-dependent Cellular Cytotoxicity) or CDC (Complement-dependent Cytotoxicity). Additional studies done with AbGn-168, which support the safety assessment of AbGn-168H include the demonstration that no apoptosis induction occurs in other PSGL-1 expressing cells, including neutrophils, B cells and monocytes, after AbGn-168 treatment. *In vitro* binding by AbGn-168 does not interfere with

the interaction of P-selectin with PSGL-1, a key function associated with PSGL-1 and a requirement for efficient localization of activated T cells and neutrophils to target tissues. In addition, there is no *in vitro* cytokine release from purified CD4+ T cells or PBMC when treated with AbGn-168 or AbGn-168H (see also [Toxicology](#)). Furthermore, administration of AbGn-168H surrogate antibody in mice (cTAB4) does not have significant impact on the disease progression of *C. difficile* infection.

Toxicology

AbGn-168H toxicity evaluations include studies supporting the use of the cynomolgus monkey as the toxicologically relevant species, a study investigating the potential for cytokine release in humans, and 4-week intravenous and subcutaneous repeat-dose toxicity studies in cynomolgus monkeys. Relevant studies with AbGn-168 which support the safety assessment of AbGn-168H include additional cytokine release studies, intravenous repeat-dose toxicity evaluations up to 13 weeks with a 39-week recovery period, evaluation of effects on the hematopoietic system (including stem cells and platelet), and local tolerance assessment.

AbGn-168H administered over 4 weeks by twice weekly intravenous infusion or subcutaneous administration to cynomolgus monkeys caused no adverse effects at dose levels up to 100 mg/kg, and administration of AbGn-168 twice weekly at dose levels up to 100 mg/kg for 4- or 13 weeks likewise caused no adverse effects in monkeys. The 13-week repeat-dose study in cynomolgus monkeys with AbGn-168 showed no effect on a T-cell dependent antibody response or on NK cell cytolytic activity. **Therefore, the No Observable Adverse Effect Level (NOAEL) of AbGn-168H was greater than 100 mg/kg, twice per week.**

There was no evidence of any treatment-related effect *in vivo* on circulating cytokines in the 4-week studies with AbGn-168H or AbGn-168, or in a separate DTH monkey study with AbGn-168 that simulated the conditions of an activated immune system. In addition, there was no evidence for *in vitro* cytokine release in whole blood from healthy donors exposed to AbGn-168H or AbGn-168, or in whole blood from psoriatic patients exposed to AbGn-168. Taking the results from all of these studies together, the weight of evidence suggests that treatment with AbGn-168H in humans has a low risk of inducing cytokine release.

Studies to test the potential effects of AbGn-168 on bone marrow demonstrated that AbGn-168 binds to human and cynomolgus monkey CD34+ stem cells but does not appear to affect hematopoiesis. The effect of AbGn-168 on platelet function was evaluated and data showed that AbGn-168 did not bind platelets that were either untreated or thrombin activated.

AbGn-168H was well tolerated locally in cynomolgus monkeys when administered by repeated intravenous or subcutaneous administration twice per week over 4 weeks. AbGn-168 formulation, very similar to that of AbGn-168H, was well tolerated locally in cynomolgus monkeys at concentrations of 10 and 40 mg/mL when administered by intravenous, intramuscular, and subcutaneous routes. AbGn-168 did not cause hemolysis of human whole blood *in vitro* and was compatible with human plasma.

AbGn-168H is immunogenic in cynomolgus monkeys. Repeat dose administration of AbGn-168H to cynomolgus monkeys resulted in an immunogenic response. However, such immunogenicity does not appear to have been a seriously limiting factor for other humanized monoclonal antibodies taken into the clinic.

No developmental or reproductive toxicology studies have been conducted to date. No treatment-related effects on the reproductive tissues of male and female monkeys when administered AbGn-168H for up to 4 weeks or AbGn-168 for up to 13 weeks were observed, with the caveat that many of these animals were sexually immature. Based on the biophysical nature of monoclonal antibodies and the demonstrated mode of action for AbGn-168H, genetic toxicology studies are not warranted and have not been performed. Carcinogenicity studies have not been conducted to date.

Non-clinical Pharmacokinetics

The pharmacokinetics of AbGn-168H was studied in CD57BL/6 mice and cynomolgus monkeys and was compared with the pharmacokinetics of AbGn-168 in those species. Exposures for AbGn-168H were quite similar to those for AbGn-168 in these studies. Whereas AbGn-168 undergoes IgG₄ shuffling in cynomolgus monkeys, AbGn-168H exhibits little if any IgG₄ shuffling.

In the 4- and 13-week studies with AbGn-168H and AbGn-168, the highest dose level tested of 100 mg/kg was a NOAEL. At the NOAEL, AbGn-168H mean exposures on Day 25 in the 4-week intravenous study were approximately 5,230,000 ng/mL (C_{max}) and 308,500,000 ng-hr/mL (AUC_{0-72hr}) and mean exposures on Day 22 of the 4-week subcutaneous study were approximately 4,450,000 ng/mL (C_{max}) and 353,000,000 ng-hr/mL (AUC_{0-96hr}). Exposure levels of AbGn-168H in the 4-week study were comparable to levels of total AbGn-168 (intact + shuffled) in 4- and 13-week studies. The results of the 4-week studies in cynomolgus monkeys with AbGn-168H, including exposure levels, mirror those of 4- and 13-week repeat-dose toxicity studies with AbGn-168.

Clinical Studies

AbGn-168H was first tested in a single rising dose (SRD) **trial (Study 1304.1)**[\[49\]](#) in 36 healthy volunteers in doses up to 2000 µg/kg i.v. and 125 and 1000 µg/kg s.c.. AbGn-168H was well tolerated in the SRD trial. There was no evidence of cytokine release and no critical change in laboratory parameters.

The PK analysis of trial 1304.1 demonstrated that no shuffling with AbGn-168H occurred. After i.v. dosing, AbGn-168H C_{max} or $AUC_{0-\infty}$ exposure increased in a close to dose-proportional manner. The terminal half-life of the antibody increased somewhat with dose up to the 500 µg/kg dose and then remained relatively constant at higher doses (40-45 h), which is relatively short compared to published values of endogenous IgG₄ half-life. This suggests that AbGn-168H may be cleared by target-mediated clearance. Following s.c. dosing, bioavailability for the 125 µg/kg

and 1000 µg/kg s.c. doses of AbGn-168H is 33% and 42%, respectively. These values may be relatively low because of the relatively rapid clearance of AbGn-168H. In trial 1304.1, Anti-Drug Antibody (ADA) responses were only observed in 1 subject dosed at 125 µg/kg s.c. AbGn-168H.

Multiple doses of AbGn-168H were first tested in two randomized, double blind, placebo-controlled Phase II studies in patients with moderate to severe chronic plaque psoriasis (**Study No. 2012.005.01** and **Study No. 2014.002.01**)[\[45\]](#), [\[46\]](#). In **study 2012.005.01**, six consecutive weekly doses of AbGn-168H at 0.5 mg/kg (19 patients) or 3 mg/kg (18 patients) were well tolerated. There was no evidence of cytokine release or any critical change in lab parameters, although a mild, clinically insignificant, transient, and reversible decreases in the mean and median total leukocyte counts were observed in the 3 mg/kg group. Signs of clinical efficacy (median PASI score over time, % of PASI50 responders, and improved TLPSS assessment) were observed at 3 mg/kg compared to Placebo group. **Clinical proof of principle was considered demonstrated in psoriasis** [\[45\]](#).

Analysis of the pharmacokinetic parameters for AbGn-168H revealed that increasing the concentration of AbGn-168H from 0.5 mg/kg to 3 mg/kg disproportionately increased both the plasma concentration (C_{max}) and the exposure (AUC). Of the 19 patients in the AbGn-168H 0.5 mg/kg group and the 18 patients in the AbGn-168H 3 mg/kg group, 3 (15.8%) patients in the AbGn-168H 0.5 mg/kg group and 7 (38.9%) patients in the AbGn-168H 3 mg/kg group were confirmed positive for ADA (titer \leq 625) at one or more visits.

In **Study 2014.002.01**, 4 doses of 6 mg/kg (17 patients) and 9 mg/kg (16 patients) given to patients with moderate to severe chronic plaque psoriasis on Day 1 (W0), Day 8 (W1), Day 29 (W4) and Day 36 (W5) was well tolerated. There was no evidence of cytokine release or any critical change in lab parameters, although a mild, clinically insignificant, transient and reversible decreases in the mean and median total leukocyte counts were observed in both the 6 mg/kg and 9 mg/kg groups. Although results for the primary efficacy endpoint, the frequency of PASI75 at Week 10, were unremarkable, a consistently greater number of patients in the AbGn-168H groups achieved a PASI50 compared with the placebo group at every assessment time point except Week 1 (for the 9 mg/kg group compared with placebo) and Week 5 (for the 6 mg/kg group compared with placebo). **Clinical proof of principle is considered proven once again for psoriasis** [\[46\]](#).

Analysis of the pharmacokinetic parameters for AbGn-168H revealed that increasing the concentration of AbGn-168H from 6 mg/kg to 9 mg/kg increased both the plasma concentration and exposure (approximately 2.8 times). The steady-state $T_{1/2}$ was also increased from 113.9 hr in the AbGn-168H 6 mg/kg group to 132.1 hr in the AbGn-168H 9 mg/kg group. Of the 17 patients in the AbGn-168H 6 mg/kg group and the 16 patients in the AbGn-168H 9 mg/kg group, 4 (23.5%) patients in the AbGn-168H 6 mg/kg group and 5 (31.2%) patients in the AbGn-168H

9 mg/kg group were confirmed ADA positive at some time during the study. The ADA titer was generally low (≤ 3125) with the exception of 1 patient in the 9 mg/kg group who had an ADA titer of 15625 at Week 20.

Study 2014.009.01 is a phase II open-label, multi-center, proof of principle trial for psoriatic arthritis in which Seven (7) doses of AbGn-168H at 9 mg/kg was administered in 20 patients with moderately to severely active psoriatic arthritis. AbGn-168H were well tolerated and no safety concerns for AbGn-168H administration at this dose. Forty percent (40%) of all patients treated with study agent in this open label study demonstrated meaningful responses by week 12, suggesting the clinical utility with AbGn-168H for the treatment of psoriatic arthritis. **Clinical proof of principle is considered proven also for psoriatic arthritis [47]**. There was only one positive ADA response (Ab titer is 125) detected at Week 12 from 1 patient who had received all 7 doses of the study drug.

Since AbGn-168H demonstrated proof of clinical principle in treating T-cell mediated diseases such as psoriasis and psoriatic arthritis, a dose escalation/de-escalation study using AbGn-168H to treat steroid-refractory acute graft-versus-host disease (sr-aGvHD) in patients undergoing allogeneic hematopoietic cell transplantation was initiated (**Study BMT-285**). Patients received up to 4 infusions of up to 9 mg/kg of AbGn-168H. Four (4) patients were enrolled and received at least one infusion of AbGn-168H.

The AEs observed in this small group of patients were consistent with what would be expected in this patient population. The most frequently occurring AEs were diarrhea (n=3), elevated bilirubin levels (n=3), ileus (n=2), septic shock (n=2) and respiratory distress (n=2). There were no cytokine release reactions or infusion reactions observed with AbGn-168H and there was no apparent association between increasing dose of AbGn-168H and increasing incidence or severity of adverse events. No DLTs attributed to AbGn-168H were observed in this study. Three patients died during the study due to complications arising from disease progression of severe aGvHD.

The mortality in this study triggered an accrual pause to conduct safety review by protocol, and was subsequently placed on Clinical Hold by the FDA on April 8, 2016, although the continuation of the study was concurred by the Institute DSMC. After a face-to-face discussion with FDA on Nov. 15, 2016, a newly designed study protocol (Study 2017.002.01) was resubmitted on May 1, 2017. May proceed letter was received on May 18, 2017 and the study is currently ongoing.

This **Study 2017.008.01** is a Phase II, open label, single arm, multiple dose proof of principle study to test the therapeutic effect of Neihulizumab in patients with moderate to severe ulcerative colitis and who has failed or are intolerant to anti-TNF α and/or anti-integrin therapy. This study is to be conducted in compliance with Good Clinical Practice (GCP). For further details see “Investigator’s Brochure”[50].

2. RATIONALE, OBJECTIVES, AND BENEFIT-RISK ASSESSMENT

2.1 RATIONALE FOR PERFORMING THE TRIAL

Therapeutic rationale for AbGn-168H in anti-TNF α and/or anti-integrin refractory ulcerative colitis

As discussed previously, the pathological process that causes mucosa damage in ulcerative colitis is substantially involved with T cell accumulation and T cell mediated immune-inflammatory response. The important role of T cells in the pathogenesis of ulcerative colitis has been suggested in the literature and therapies that target T cell mediated inflammatory response and T cell trafficking have demonstrated efficacy to treat UC[24]–[28]. However, with all the biologics available to date, more than 50% of UC patients failed to reach remission and hence a new therapeutic agent with a different mode of action is required for this unmet medical need. Anti-TNF α and/or anti-integrin agents are the major biologics available in UC treatments and therefore patients who are refractory to these two types of biologics are selected as the target population for this study.

AbGn-168H is an agonistic mAb to PSGL-1 (CD162) which has been shown to induce apoptosis of late-stage activated T-cells *in vitro* but spare naïve T cells and other hematopoietic cells. This mode of action can be applied in UC to target this specific T-cell population which is driving pro-inflammatory reactions but spares those naïve T cells which are for protective immunity, so without increasing the risk of infections. AbGn-168H showed *in vivo* efficacy in the *trans-vivo* DTH models which are models of T-cell dependent inflammatory disease. Clinical proof of principle is also obtained in T cell-mediated diseases such as psoriasis and psoriatic arthritis. All these results justify the adding on of AbGn-168H in the treatment of ulcerative colitis.

Justification for doses

The highest dose of AbGn-168H used in the 4-week intravenous and subcutaneous toxicity studies (100 mg/kg; twice weekly) was also the NOAEL. [Table 4](#) depicts safety margins extrapolated from 4th doses of AbGn-168H in humans (Study 2012.005.01 and Study 2014.002.01) *versus* the monkey NOAEL weekly dose and systemic exposure after 4-weeks of intravenous dosing. Although an adverse effect level was not reached with AbGn-168H in monkeys, it is clear that safety margins projected for the highest dose of 9 mg/kg based on body weight dose, C_{max}, and AUC comparisons for patients in this Phase I trial should be considered adequate. Safety evaluation from Study 2014.009.01 which was only 1 dose less than dosing regimen proposed in study also substantiates the safety of the current 8 dose regimen.

Table 4 Safety Margins from 4-Week Monkey Study (IV) with AbGn-168H estimated based on trial 2014.002.01

Species	Route of Admin	Maximum Dose	Weekly Dose	Dosing duration	C _{max} (ng/mL)	AUC (ng·hr/mL)	Safety Margins Vs Maximum Human Dose		
							Weekly Dose	C _{max}	AUC
Monkey	IV	100 mg/kg	200 mg/kg	4 weeks	5,230,000	308,500,000			
Human Patients	IV	9 mg/kg	9 mg/kg	8 weeks	751,750*	151,862,500*	>22X	>6X	>2X

*extrapolated data from 4st doses in Phase II studies (Study 2014.002.01) in psoriatic patients at 9 mg/kg iv.

2.2 TRIAL OBJECTIVES

The **primary objective** is to evaluate efficacy of AbGn-168H administered intravenously in patients with moderate-to-severe active ulcerative colitis who are refractory or intolerant to anti-TNF α and/or anti-integrin treatments.

The **secondary objective** of this study is to investigate safety, tolerability, and immunogenicity of intravenous AbGn-168H administration.

2.3 BENEFIT - RISK ASSESSMENT

With this novel mechanism of action Neihulizumab is anticipated to be effective in treating T-cell mediated autoimmune diseases. In both Studies 2012.005.01 and 2014.002.01, signs of efficacy were clearly observed for psoriasis. Study 2014.009.01 also demonstrated clinical efficacy for psoriatic arthritis (see [Section clinical studies](#)). Patients of UC might benefit from the trial because T cells play a pivotal role in the pathogenesis of UC, and based on Neihulizumab's novel mechanism of action it is expected that patients with UC are going to benefit from the treatment of Neihulizumab.

Risk of hematopoietic cell depletion

In Study 1304.1, Study 2012.005.01, Study 2014.002.01 and Study 2014.009.1, Neihulizumab single or multiple doses were well tolerated. No cytokine release syndrome or hematopoietic cell depletion was observed in these four studies. A mild, clinically insignificant, transient, and reversible decrease in the mean and median total leukocyte counts was observed in the 3 mg/kg group in trial 2012.005.01 and in the 6 mg/kg and 9 mg/kg groups in trial 2014.002.01, and in study 2014.009.01 where 7 doses of Neihulizumab at 9 mg/kg were administered. Although the risk that Neihulizumab will affect stem cells is convincingly low, it is still critical that careful long-term monitoring of peripheral blood cells is carried out to rule out a clinically significant adverse effect of Neihulizumab on bone marrow stem cells *in vivo*.

Risk of impaired immune function

Neihulizumab has been demonstrated to induce apoptosis selectively in late stage activated T-cells. This selectivity suggests that naïve and resting memory T-cells would be spared from deletion by Neihulizumab, and therefore that Neihulizumab may be less immunosuppressive than pan-T-cell depleting mAbs or the systemic immunomodulating agent such as cyclosporine. However, it cannot be ruled out that depletion of activated T-cells by Neihulizumab may lead to a transiently increased risk of infection. This risk will be addressed by clinical monitoring for adverse events during the treatment and observation periods.

Treatment of psoriasis and psoriatic arthritis with systemic immunomodulatory therapies such as TNF α antagonists has been associated with an increased risk of tuberculosis, and as a result, current guidelines recommend screening patients for latent tuberculosis infection prior to treatment with such agents. As it is not known if a similar risk would be posed by Neihulizumab administration, patients with tuberculosis, history of tuberculosis, or a positive Quantiferon test will be excluded ([Exclusion Criterion 24](#)).

Risk of hypersensitivity reactions

As with any systemically administered biologic agent, there is a risk of local or systemic hypersensitivity reactions. Local reactions to intravenously or subcutaneously administered biologic agents are uncommon, and are usually limited to redness, swelling or induration at the injection site. Manifestations of systemic hypersensitivity reactions include anaphylaxis, pruritus, hypotension, and respiratory distress, but these occur uncommonly. Both local and systemic hypersensitivity reactions are readily detectable, transient in nature, and manageable with standard medical treatment. No such events occurred in Neihulizumab related trials (trials 1304.1, 2012.005.01, 2014.002.01, 2014.009.01 and trial BMT-285) up to date.

Summary of benefit-risk assessment

Patients might benefit from the trial, because it is expected that UC may improve. The risks of participation in the trial include the risks associated with the study procedures (e.g. blood drawing and i.v. infusion) which are similar to other trials of investigative agents. The specific risks that can be anticipated in patients receiving Neihulizumab are described above. The study has been designed and will be conducted in such a manner as to minimize these risks as much as possible. Therefore, the benefit-risk assessment is considered acceptable for the current multiple dose trial in human.

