6.1.2 Study period

Patients who meet the inclusion/exclusion criteria will receive one dose of Neihulizumab intravenously starting from Day 1 (Week 0). It is preferred but not required that the drug administration should occur at the similar time of each visit day. See [Appendix 10.1](#) for the detailed procedures for preparing Neihulizumab for intravenously administration. Administration of the study drug will be repeated on Day 8 (Week 1), Day 15 (Week 2), Day 22 (Week 3), Day 29 (Week 4), Day 36 (Week 5), Day 43 (Week 6), Day 50 (Week 7), Day 64 (Week 9), and Day 78 (Week 11).

The measurements performed during the study period are specified in [Section 5](#) of this protocol and [Table 1](#).

All assessments should be performed prior to drug administration unless it is specified.

Visit 2/Day 1

Procedures at Visit 2/Day 1 should preferably be done in the sequence specified. Drug administration and blood sampling should adhere as closely as possible to the time schedule given in [Table 1](#)

- Urine pregnancy test, if applicable
- Review of inclusion and exclusion criteria
- Collect the filled diary card from patient
- Physician Global Assessment
- Partial Mayo Clinic Score assessment
- Concomitant medications
- Adverse events
- Full physical examination including weight and vitals
- Safety lab tests (Hematology and Chemistry)
- Urinalysis
- Blood sampling for anti-drug antibody (ADA) test at -15 min (prior to Neihulizumab infusion)
- PK sampling: -15min (prior to Neihulizumab infusion), and 2 hrs after the end of Neihulizumab infusion

- Administration of Neihulizumab: Study drug will be administered by approximately 1hr (60-minute) i.v. infusion. Patients should remain at the clinical site for at least 1 hour after the infusion for observation.

Visit 3/Day 8, Visit 4/Day 15, Visit 5/Day 22, Visit 7/Day 36, Visit 8/Day 43, Visit 9/Day 50, and Visit 11/Day 78

- Urine pregnancy test, if applicable
- Concomitant medications
- Adverse events
- Partial physical examination including, weight and vitals
- Collect the filled diary card from patient
- Physician Global Assessment
- Partial Mayo Clinic Score assessment
- Safety lab tests (Hematology and Chemistry)
- PK sampling: -15min (prior to Neihulizumab infusion) and 2 hrs after the end of Neihulizumab infusion for Visit 9 and 11. Fifteen (15) minutes prior to Neihulizumab infusion for Visits 3, 4, 5, 7 and 8

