5.10.5 Vital Signs, Physical Examination and ECG

Over-time summary statistics (n, mean, SD, median and range) of vital signs (temperature, heart rate, respiratory rate, and systolic/diastolic blood pressure) will be provided for each scheduled visit. A separate summary will be produced for vital signs at baseline, maximum, minimum, change to maximum, change to minimum, last value, and change to last value.

Baseline physical examination findings will be summarized. New or worsened physical examination abnormalities will be analyzed as adverse events (AEs).

Descriptive statistics of ECG parameters (heart rate, PR interval, QRS interval, QT interval, and QT_C interval) will be presented.

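### No vital signs are scheduled after any of the 10 infusions, so the SAP's vital-sign summaries cannot show acute, transient infusion effects

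*Protocol*

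**What the plan says.** **What is expected of a reaction.** Protocol section 2.3 states: "Manifestations of systemic hypersensitivity reactions include anaphylaxis, pruritus, hypotension, and respiratory distress, but these occur uncommonly". It adds: "Both local and systemic hypersensitivity reactions are readily detectable, transient in nature, and manageable with standard medical treatment".

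**Why vital signs matter here.** Section 2.2 makes safety and tolerability of intravenous dosing part of the secondary objective. Section 5.2.1 lists change in vital signs as a safety endpoint.

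**When they are taken.** Section 6.1.2 sets a default: "All assessments should be performed prior to drug administration unless it is specified". For the first dosing visit it adds: "Procedures at Visit 2/Day 1 should preferably be done in the sequence specified". In that list, "Full physical examination including weight and vitals" comes before the infusion item. The list for Visits 3, 4, 5, 7, 8, 9 and 11 has "Partial physical examination including, weight and vitals", again before the infusion, and the list for Visits 6 and 10 has the same item in the same position. The infusion item at each dosing visit ends: "Patients should remain at the clinical site for at least 1 hour after the infusion for observation". No measurement is named for that hour. Table 1 marks vital signs once per visit, with no timing footnote.

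**How they are reported.** SAP 5.10.5 gives summary statistics for each scheduled visit and then: "A separate summary will be produced for vital signs at baseline, maximum, minimum", with the changes to those extremes and to the last value. SAP 5.5 sends unscheduled vital signs, including those taken while an adverse event is being worked up or treated, to listings and keeps them out of summaries.

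**The concern.** A blood-pressure fall that starts during an infusion and settles the same day would lie between two scheduled readings. If staff did take a reading because the patient was unwell, SAP 5.5 would exclude it from the maximum, minimum and change table, where a reader would look for it. A flat vital-sign table would then follow largely from when the readings were taken and which were summarised, yet could be quoted in the study report as support for tolerability of the infusion. Infusional toxicity is one of the two adverse events of special interest (protocol 5.2.2.1.1), so that misreading would bear on a main safety question of the trial.

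**Working it through.** The plan states no figure for this point. The check applies the timing rule to each dosing visit, computes the gaps, and then follows the readings into the SAP tables.

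**1. Is there an exception to the pre-dose default?** The protocol does state a post-infusion time where it wants one: PK sampling 2 hours after the end of infusion at Visits 2, 9 and 11 (Table 1 footnote 9; section 6.1.2). No such statement exists for vital signs in Table 1, its footnotes or the visit lists. Result: 0 of 10 dosing visits have a scheduled post-infusion vital-sign reading.

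**2. How long until the next scheduled reading?** Gap = day of next visit minus day of infusion, using the nominal days in Table 1 (Amendment 4).

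| Doses | Infusion days | Next visit days | Gap (days) |
|---|---|---|---|
| 1-7 | 1, 8, 15, 22, 29, 36, 43 | 8, 15, 22, 29, 36, 43, 50 | 7 each |
| 8 | 50 | 64 | 14 |
| 9 | 64 | 78 | 14 |
| 10 | 78 | 84 | 6 |

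The windows are ±1 day at Day 78 and ±2 days at Day 84, so the shortest permitted gap is (84 − 2) − (78 + 1) = 3 days.

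For patients enrolled under Amendments 1-3 (SAP Appendix 2: doses on Days 1, 8, 15, 22, 29, 43, 57 and 71, then Day 84), the gaps are 7 days for doses 1-4, 14 days for doses 5-7, and 84 − 71 = 13 days for dose 8. This assumes the same pre-dose default applied; the text of those amendments is not available here.

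**3. What do the SAP 5.10.5 tables contain?**
- Rows for Weeks 0-11: readings taken before that day's infusion.
- Rows for Weeks 12, 16, 20 and 26: readings at visits with no infusion.
- Maximum, minimum and change: drawn from the same scheduled readings, because SAP 5.5 removes adverse-event readings from all summaries.

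No row is planned to hold a reading taken within hours after an infusion.

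**4. Which signs are covered?** Protocol section 5.5 counts oxygen saturation as a vital sign. SAP 4.2.2.3 and 5.10.5 list temperature, heart rate, respiratory rate and blood pressure, and omit it, although section 2.3 names respiratory distress as a manifestation.

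**The case against.** The strongest reply is that infusion reactions are meant to be caught clinically, not in a vital-sign table. Patients are observed on site after every infusion. Section 5.2.2.3 assesses infusion-related reactions as a combined adverse-event incidence, with CTCAE grading and a rule that pauses enrolment. Section 5.2.5.1 requires prompt reporting of events of special interest, section 5.2.5.4 turns clinically relevant vital-sign changes into adverse events, and SAP 5.10.3 summarises the events of special interest. All of this stands. A reader might infer that section 2.3 is undermined or that reactions would go undetected. The documents do not support that: section 2.3 never ties detectability to scheduled vital signs, and these routes do not depend on them.

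A reader might also infer that post-infusion vital signs are never measured. That goes too far. Extra readings are not forbidden, and SAP 5.5 expects some and lists them. The accurate statement is that none is scheduled and that those tied to an adverse event are not summarised.

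It is also fair that no sentence times vital signs specifically. The placement rests on a general default worded as a recommendation, and on list order, which is only preferred and only at Visit 2. List order alone is weak evidence, since the adverse-event item also precedes the infusion although events are collected afterwards. The default rule carries the weight, supported by the absence of any exception.

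Finally, every reading after dose 1 follows earlier infusions, so sustained or cumulative change can still be seen.

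**Conclusion.** The point holds for the planned vital-sign summaries and for acute, transient effects only. On the Amendment 4 schedule, 0 of 10 infusions are followed by a scheduled reading on the same day. The nominal wait is 6 to 14 days, and at least 3 days within the windows. Together with the SAP 5.5 exclusion, this makes the SAP 5.10.5 tables uninformative about short-lived infusion effects, on a stated safety endpoint.

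The conclusion assumes that sites follow the section 6.1.2 default, and that a reaction resolves before the next visit, as section 2.3's own description suggests. No upper bound on an event rate is attached, because the documents define no vital-sign event to which one would apply. It would also be wrong to call every row of the tables pre-infusion: the Week 12-26 visits have no infusion. This is an inexpensive improvement to data capture and reporting; it does not show that the trial's detection of infusion reactions fails.

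**What to change.** - **Protocol.** Reconcile sections 2.3, 5.2.1 and 6.1.2 and Table 1 with SAP 5.5 and 5.10.5. The sponsor should state whether vital signs are taken in the existing observation hour. If they are, exempt them from the pre-dose default and record them as a time point, at a time the sponsor sets.
- **SAP 5.5 and 5.10.5.** Include dosing-day post-infusion readings and adverse-event readings in the maximum, minimum and change table. Report change from before to after the infusion by dose number where both readings exist. Add oxygen saturation here and in SAP 4.2.2.3, to match protocol section 5.5.
- **If no post-infusion readings exist.** Label the Week 0-11 rows as pre-infusion, leave Weeks 12-26 as they are, and do not cite the dosing-visit rows as evidence of acute infusion tolerability.

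Cost: one extra data field per infusion and one extra table. SAP 4.1 says the study has been closed out, so a protocol change cannot create readings that were not taken; for this dataset only the SAP and labelling changes can act. Those need wording and programming but no new data.
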